**RESEARCH REFERENCE NUMBERS (SWAP SUB STUDY):** 

Health Research Authority approval: IRAS project ID; REC refence: [pending]

FUNDING:

This study has been funded by NIHR HS&DR SWAP funding.

### **STUDY FLOW CHART:**

### A1.0 Context

Joint pain, osteoarthritis (OA), obesity, and type 2 diabetes (T2D), are common diseases that frequently coexist as Multiple Long Terms Conditions (MLTC)[1]. Many patients taking part in the NHS Low Calorie Diet (LCD) programme will have co-existing obesity, T2D and OA. Our patient advisory group is concerned about the impact of co-existing OA and pain, on LCD patient experience and success. This concern is further substantiated by existing research evidence that suggests: 1) a bidirectional relationship between weight and pain that may impact weight loss[2, 3]; 2) that systemic inflammation, found in obesity and diabetes, may be involved in the development and progression of OA pain[4, 5]. This study presents a unique opportunity to further understand the impact of OA pain on patient experience and inflammatory biomarkers, that will provide critical understanding as to how best to tailor programme support for this patient group.

### A1.1 Rationale

Although previous trials have examined the role of LCD programmes delivered through total diet replacement products for OA[6], obesity[7] and T2D[8] none have examined the impact on lived experience and underlying inflammatory mechanisms, specifically in patients with all three conditions. There is currently a gap in terms of the most appropriate support for patients with obesity, T2D and OA as MLTC.

A number of pathological drivers have been postulated to cause OA pain, including local factors (such as cartilage loss and local inflammation) and systemic factors, but these relationships remain unclear. This study will enable us to examine the lived experience, joint symptoms and systemic inflammatory profile of a cohort of patients with obesity and T2D with and without co-existing OA. The findings will provide new insights into the impact of the LCD programme in patients with co-existing OA, and whether the current programme can be tailored to enhance support and success within this patient group.

### A2.0 Research Aims and Objectives

### Aim:

To collect additional qualitative data and clinical biomarkers to understand the impact of LCD in patients with MLTC: obesity, T2D and painful OA of the hip or knee.

### **Objectives:**

- 1.To undertake ten additional longitudinal interviews, using novel adapted photovoice methodology to explore the lived experience of the LCD programme in patients with co-existing OA, to explore how this may impact on their ability to participate in the programme and whether additional support needs are required.
- 2. To assess IL-6 and hs-CRP in LCD patients with and without OA to determine the impact of the programme on underlying inflammatory pathways.
- 3. Use learning from this study to inform practice and research:
  - a. Develop additional support for LCD patients with MLTC if required.
  - b. Inform the development of personalised approaches to diabetes management

### A3.0 Study Design

This study will be a sub study of the main Re:Mission study evaluation, that will use a mixed methods approach to provide new data that will further our understanding of the relationship between hs-CRP and joint pain, underpinning targeted therapy and providing new treatment options for this well-defined subset of patients with OA. The study will therefore provide outcomes that will directly inform other pain and inflammatory research; inform the care of patients with T2D and obesity, and further inform the NHS LCD evaluation.

This work will be undertaken in two work packages, to answer the following research questions:

- What are the lived experiences of Low Calorie Diet programme participants who have coexisting OA pain?
- What is the relationship between success of the Low Calorie Diet programme and inflammatory biomarkers?
- Can the management of participants on the Low Calorie Diet programme with pre-existing OA pain, be improved?

### A4.0 Methods

### A4.1 Work Package A: Quantitative research

In this work package we will examine the impact of joint pain in people taking part in the NHS Low Calorie Diet programme

### A4.1.1 Target population

100 patients with and 100 patients without OA of the hip or knee from the NHS LCD programme cohort.

Participants will be allocated to the OA or Non-OA cohort using the following screening question: Has your GP ever referred you to see a specialist [physio, orthopaedic, rheumatology] about pain in your hip or knee, or have you been told you have OA of the hip or knee? Participants who answer yes to either question and have not undergone a hip or knee replacement in their OA hip/s and/or knee/s (i.e. have at least one native hip or knee affected by OA), will be enrolled into the 'OA cohort'. Participants who answer no to both questions will be enrolled into the 'Non-OA cohort'.

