### OA participants only:

(a) At least one native hip or knee affected by OA

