### Exclusion criteria

(a) Any physical or mental condition or disorder, which, in the opinion of the investigator, may affect participation in the study.

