### A4.1.4 Informed consent

In all instances, potential participants will be given as long as they need, ideally at least 24 hours, to consider participation and will be given the opportunity to discuss the study with their family and healthcare professionals before being invited to give consent to participate in the study.

Assenting participants will then be formally assessed for eligibility by the PI or authorised delegate as listed on the trial specific delegation log and invited to provide informed, written consent. The right of the patient to refuse consent without giving reasons will be respected. A copy of the consent will be given to the participant, and one filed in the Study Files. The written consent will be taken by the PI or authorised delegate, who has signed / dated the staff authorisation / delegation log.

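### A past GP referral for hip or knee pain is enough for the OA cohort, with no stated way of establishing OA or recording inflammatory arthritis, so the with/without OA description of hs-CRP and IL-6 is at risk of bias of unknown size and direction

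*Protocol*

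**What the plan says.** All references are to Annex 1 of the Protocol.

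- **Aim (A2.0).** The population of interest is patients with "obesity, T2D and painful OA of the hip or knee". Objective 2 looks at IL-6 and hs-CRP in programme patients with and without OA.
- **Allocation (A4.1.1).** There are two limbs. The first is "Has your GP ever referred you to see a specialist [physio, orthopaedic, rheumatology] about pain in your hip or knee". The second is "or have you been told you have OA of the hip or knee". The combination rule is "Participants who answer yes to either question and have not undergone a hip or knee replacement in their OA hip/s and/or knee/s", and the sentence continues with a gloss: "i.e. have at least one native hip or knee affected by OA), will be enrolled into the 'OA cohort". A no to both limbs puts the person in the Non-OA cohort.
- **Eligibility (A4.1.2).** OA participants must have "At least one native hip or knee affected by OA". The only exclusion is "Any physical or mental condition or disorder, which, in the opinion of the investigator, may affect participation in the study".
- **Eligibility check (A4.1.4).** "Assenting participants will then be formally assessed for eligibility by the PI or authorised delegate". The visit schedule (A4.1.6) lists consent, inclusion/exclusion, questionnaires and a blood sample. It has no examination, imaging or record check for OA.
- **Use of the label.** A4.1.8.3 plans estimates of the prevalence of systemic inflammation, and correlations, by cohort. A4.1.8.4 anticipates 100 people per cohort and states that no power calculation was done. A4.2 draws ten interviewees from the OA cohort.

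**The concern.** The first limb asks about a referral at any time, for pain, to any of three services. It does not ask about OA. Someone once sent to physiotherapy for a knee strain, or to rheumatology for an inflammatory arthritis, can answer yes truthfully and never have been told of OA. The gloss then describes that person as having a joint affected by OA, which does not follow from the answer.

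Cohort membership is the grouping variable for Objective 2 and for the cohort summaries in A4.1.8.3. Followed as written, the allocation compares people ever referred for hip or knee pain or told of OA with people who were neither. That is a different grouping from OA versus no OA. People with pain but no OA would pull a true difference towards zero. People with inflammatory joint disease would raise the OA cohort's marker levels for a reason other than OA.

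There is also a practical gap. A4.1.5.1 assigns KOOS or HOOS according to which joint has OA, and this is undefined for someone who was only referred.

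**Working it through.** **1. The texts side by side.**

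| Place | Condition for the OA cohort |
|---|---|
| A2.0 | painful OA of hip or knee |
| A4.1.2 | a native joint affected by OA; method not stated |
| A4.1.1 | referred for pain at any time, or told of OA; joint not replaced |

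A referred-only person satisfies the third row and need not satisfy the first two. The no-replacement condition concerns whether the joint is native and does not bear on diagnosis.

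**2. The plan's own figure.** 100 + 100 = 200, which agrees with A4.1.8.4. With no power calculation, there is no effect size, SD or misclassification rate to reproduce. Everything in steps 3 to 6 rests on assumed values.

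**3. Dilution (illustration).** Let f be the share of the OA cohort without OA, assumed to have non-OA marker levels, and d the true difference in SD units. Observed difference = d × (1 − f). Power is for 100 per cohort, two-sided 5%, normal approximation: Φ(observed × √50 − 1.96). With d = 0.40:

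| f | Observed difference (SD) | Power | n per cohort for 80% power |
|---|---|---|---|
| 0% | 0.40 | 0.81 | 99 |
| 10% | 0.36 | 0.72 | 122 |
| 20% | 0.32 | 0.62 | 154 |
| 30% | 0.28 | 0.51 | 201 |
| 40% | 0.24 | 0.40 | 273 |

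**4. Inflation (illustration, levels at one time point).** Let a share g of the OA cohort have inflammatory joint disease with markers S SD higher, and let OA itself have no effect. Spurious difference = g × S. The OA-cohort SD becomes √(1 + g(1 − g)S²).

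| S | g | Spurious difference (SD) | Chance of p < 0.05 |
|---|---|---|---|
| 1 | 5% | 0.05 | 6% |
| 1 | 10% | 0.10 | 11% |
| 1 | 20% | 0.20 | 28% |
| 2 | 5% | 0.10 | 10% |
| 2 | 10% | 0.20 | 26% |
| 2 | 20% | 0.40 | 69% |

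**5. Both together.** Take d = 0.40, f = 20%, and a further g = 10% with inflammatory disease instead of OA. Observed difference = 0.70 × 0.40 + 0.10 × S. For S = 1.0 this is 0.28 + 0.10 = 0.38. For S = 1.5 it is 0.28 + 0.15 = 0.43. The result falls on either side of 0.40 for a modest change in S, so the net direction is not determined.

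**6. Change from baseline to 6 months.** If the inflammatory elevation S is stable, change = (6-month level + S) − (baseline level + S), and S drops out. Step 4 therefore applies mainly to levels. Step 3 still applies to change, because a difference in change between people with and without OA is also multiplied by (1 − f).

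**The case against.** The strongest reply is that A4.1.2 separately requires a joint affected by OA and A4.1.4 has the investigator or delegate assess eligibility, so a plain knee-strain referral could be refused. That room exists, and it stops one saying that every referred person must end up in the OA cohort. It does not settle the matter: no method for the judgement is given, and A4.1.1 presents a yes to either limb as meeting the criterion.

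A reader might infer that the cohort is contaminated, or that the limbs are merged and the error can never be undone. The documents support neither. Contamination is a risk with no stated rate. A4.1.1 speaks of two questions, the case report form is not shown, and separate recording is not ruled out. Linkage to the minimum dataset (A4.1.5.3) might supply comorbidity, although whether it covers arthritis cannot be seen. The statistical analysis plan could add sensitivity analyses, but only if the needed items are collected at enrolment.

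It is also fair that the sub-study is exploratory and largely descriptive, that A4.1.8.3 names no formal OA versus non-OA biomarker test, and that its logistic regression is on symptom reporting. This limits the consequence. The cohort-specific inflammation estimates still depend on the label.

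Finally, a broad question captures people with OA who were never told. Restricting enrolment to those told of OA would trade sensitivity for specificity, so the fix leaves enrolment broad.

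**Conclusion.** The point holds as a gap between the allocation rule and the criterion it is meant to implement. A self-reported past referral alone can place someone in the OA cohort, no procedure establishes OA, and inflammatory arthritis goes unrecorded in a study of inflammatory markers. The with/without OA description of hs-CRP and IL-6 is therefore at risk of dilution and, mainly for single-time levels, of inflation.

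Neither size nor net direction follows from the documents. The SD and power figures rest on an assumed d, f, g and S, on non-OA marker levels in people with non-OA pain, and on the normal approximation. They show that plausible values could matter, not that they occur. A reader might conclude that the comparison is invalid or that OA-related inflammation will be overstated; the documents support neither.

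**What to change.** 1. Reconcile A4.1.1 with A2.0 and A4.1.2: state what counts as affected by OA, and remove the implication that a referral establishes it.
2. Record the two screening answers as separate items. Add one self-report item on diagnosed inflammatory arthritis, asked in both cohorts, since a person whose disease affects other joints can answer no to both existing questions.
3. Keep the broad cohort for enrolment. Report the OA versus non-OA biomarker comparison for told-of-OA participants, show referred-only participants as their own group, and give results with and without people reporting inflammatory arthritis.
4. Describe painful OA with the KOOS/HOOS pain items already collected. The Nordic 0-10 rating is of overall pain and does not isolate the hip or knee.

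**Cost.** The screening-form change is small, but it is a protocol amendment needing sponsor review and possibly REC/HRA approval (A5.7). The told-of-OA group will be smaller than 100. As illustration, if 20% were referred only, the comparison is 80 versus 100, with standard error √(1/80 + 1/100) = 0.15. Power for an assumed 0.40 SD is Φ(0.40/0.15 − 1.96) = Φ(0.71) = 0.76. That compares with 0.62 for the full cohort if none of the referred-only people had OA, and with 0.81 if all of them did.

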### A4.1.2 Eligibility criteria

### Inclusion criteria

- (a) Age 18 years or over
- (b) Ability to provide informed consent
- (c) Referral into NHS Low Calorie Diet programme.

### OA participants only:

(a) At least one native hip or knee affected by OA

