### (b) Adapted Nordic questionnaire (Kuorinka et al., 1987)

A standardised questionnaire designed to answer the following question: "Do musculoskeletal troubles occur in a given population, and if so, in what parts of the body are they localised?" The questionnaire includes a shaded manikin highlighting regions of the body and asks the participant to indicate which regions they experience trouble (ache, pain or discomfort). For the purposes of this study, the questionnaire has been adapted to determine if the pain is new onset post-COVID-19 and to rate the overall (average) severity of the pain in the past week on a 0-10 numerical rating scale (NRS), where 0 is no pain and 10 is pain as bad as it can be.

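### The OA sub-study asks about painful OA, but its OA cohort and its ten interviewees are selected on OA history, with no requirement for current pain

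*Protocol*

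**What the plan says.** All references are to Annex 1 of the protocol (the SWAP sub-study) unless stated otherwise.

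**What the sub-study is about**
- The aim in A2.0 names patients with "obesity, T2D and painful OA of the hip or knee".
- In A3.0, the first research question concerns "participants who have coexisting OA pain" and the third concerns "participants on the Low Calorie Diet programme with pre-existing OA pain". The second, on programme success and inflammatory biomarkers, does not mention pain.
- A4.1 introduces Work Package A with "we will examine the impact of joint pain in people taking part in the NHS Low Calorie Diet" programme.
- The Objectives are worded differently. Objective 1 concerns co-existing OA, and Objective 2 compares IL-6 and hs-CRP in patients with and without OA. Neither mentions pain.

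**How people are selected**
- A4.1.1 puts a participant in the OA cohort on a yes to either of two items: a GP referral at any time about hip or knee pain, or having been told of hip or knee OA. At least one affected joint must not have been replaced.
- "Participants who answer no to both questions will be enrolled into the" non-OA cohort.
- The only OA-specific criterion in A4.1.2 is "At least one native hip or knee affected by OA". The general inclusion and exclusion criteria do not mention pain.
- A4.2 recruits the ten interviewees from the 100 OA-cohort patients and adds no pain condition.

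**What is measured and analysed**
- The adapted Nordic questionnaire (A4.1.5.1 (b)) is completed at baseline and 6 months. It asks which body regions give trouble and asks participants to "rate the overall (average) severity of the pain in the past week on a 0-10 numerical rating scale".
- A4.1.8.3 plans a logistic regression relating case status, glossed as symptom reporting, to biomarker levels. It does not say which symptom, joint or questionnaire makes someone a case.

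**The concern.** The questions concern people who have pain now, while the selection rules ask about something that happened at any time in the past. The two can differ even if every OA label is correct.

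Two kinds of participant fall in the gap. One was told of knee OA years ago and is now comfortable; that person enters the OA cohort and can be one of the ten interviewed. The other has regular hip or knee pain but was never referred or told of OA; that person enters the non-OA cohort.

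The interviews have the most to lose. There are only ten, and an interview with someone who has no current pain cannot be repaired in analysis when the question is what it is like to go through the programme with OA pain. For the biomarkers, the risk is one of interpretation: a difference between the cohorts, or its absence, could be read as a finding about joint pain when the cohort label does not measure joint pain.

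**Working it through.** The protocol has no figure to reproduce: A4.1.8.4 says that no formal sample size or power calculation was made. The main check is to compare each question with the group selected to answer it.

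**Step 1. Question against group**

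| Element | Population or contrast in its own words | Group the rules deliver | Match? |
|---|---|---|---|
| Aim (A2.0) | Painful hip or knee OA | OA by history | No pain condition |
| Research question 1 (A3.0) | Coexisting OA pain | Ten people from the OA cohort | No pain condition |
| Research question 3 (A3.0) | Pre-existing OA pain | OA by history | No pain condition |
| Work Package A (A4.1) | Impact of joint pain | OA against non-OA by history | Label is not pain |
| Research question 2 (A3.0) | Programme success and biomarkers | Both cohorts | Pain not involved |
| Objective 1 | Co-existing OA | Ten people from the OA cohort | Yes |
| Objective 2 | With and without OA | OA against non-OA by history | Yes |

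The mismatch is therefore limited to the aim, research questions 1 and 3, and Work Package A.

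**Step 2. Do the screening items bring in current pain?** Only indirectly. The referral item mentions pain, but over a lifetime, and it is one of two alternative routes. Having been told of OA is enough without it.

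**Step 3. Which baseline measure could supply it?** KOOS and HOOS are completed according to whether the participant has knee or hip OA, so a non-OA participant with joint pain may have no joint-specific score. The Nordic questionnaire records the site of trouble and is not restricted by OA status. Its 0-10 score is described as overall severity and could reflect, for example, back pain. The site mark, not the score alone, is the usable item.

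**Step 4. Possible size, under assumptions only.** Let p be the share of the OA cohort without current hip or knee pain, and q the share of the non-OA cohort with it. The protocol gives neither. I take 10%, 20% and 30% for each as an assumed range.

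- Interviews: if selection is unrelated to pain, the expected number of pain-free interviewees is 10 × p, that is 1, 2 or 3.
- Cohort label used as a stand-in for pain: let the mean outcome be m1 with pain and m0 without, and suppose OA has no effect of its own. The cohort difference is [(1 - p)m1 + p·m0] - [q·m1 + (1 - q)m0] = (1 - p - q)(m1 - m0). The factor is 0.8, 0.6 or 0.4.
- Cells of a pain-by-OA table with 100 per cohort: the two off-diagonal cells (OA without pain, non-OA with pain) hold 10, 20 or 30 people each, and the other two hold 90, 80 or 70 each.

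The second item applies only if someone compares the cohorts and calls the result a pain effect. The protocol does not specify that comparison.

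**The case against.** The strongest reply is that the cohorts were never meant to be pain groups. The rationale, Objective 2, the target population and the sample-size section all describe an OA-status contrast, and the allocation rule delivers it. A non-OA participant with a sore knee is not misclassified there. This stands, and it is why the cohorts should not be changed.

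A second reply is that A4.1.8.3 already plans an analysis by symptom reporting, together with correlations within each cohort. These work at the level of the individual and need both painful and pain-free people, so p and q do not dilute them. A full statistical analysis plan is promised before any analysis, and a detailed case definition can properly sit there. This stands too. What remains is that case status is undefined in the text and that joint-specific scores may be lacking in the non-OA cohort.

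A third reply is that a person with OA and little pain can still describe how OA affects taking part, which is Objective 1. That is fair, but research question 1 asks about OA pain, and no rule ensures that even one of the ten interviewees has it. Selecting interviewees is a protocol matter and cannot be left to an analysis plan.

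A reader might go further and infer that the planned biomarker contrast is biased towards zero by a known amount, or that the reference group should be replaced by pain-free non-OA participants. The documents support neither. The attenuation factor rests on assumed shares and on OA having no effect apart from pain. Comparing painful OA with pain-free non-OA would confound OA with pain, would build in the baseline pain difference by selection, and could not answer Objective 2.

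**Conclusion.** The point holds as a mismatch between the pain-framed parts of the sub-study (the aim, research questions 1 and 3, and Work Package A) and selection rules that use OA history alone. It does not hold against Objective 2, which the cohorts match.

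Its weight is modest. The work is declared exploratory, makes no power claim, collects the needed information at baseline and already plans an analysis by symptoms. The clearest consequence is for the ten interviews. The effect on any pain-related biomarker result cannot be sized, because the protocol gives no pain prevalence in either cohort; the figures worked out above show only what assumed shares would imply.

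**What to change.** 1. Keep the OA and non-OA cohorts as defined, and state that they serve Objective 2.
2. In A4.2, select the ten interviewees from OA-cohort participants who mark current hip or knee trouble on the baseline Nordic questionnaire. The main protocol's interviews (WP3, Stage 2) begin at 12 weeks, so the answers will be available in time. Variation in other characteristics can still be sought within this pool.
3. In A4.1.8.3, or in the promised analysis plan, define symptom-reporting case status as current hip or knee trouble on that questionnaire, in both cohorts. Do not rest it on the 0-10 score alone, because the score is not described as specific to the hip or knee. Say what recall period the site mark refers to, since the protocol attaches the past week only to the severity score.
4. Report hs-CRP and IL-6 by OA status and by current hip or knee pain, so that the cohort label is not used as a substitute for pain.
5. Reconcile the wording of A2.0, A3.0, A4.1, A4.1.1, A4.1.2 and A4.2, so that each says whether it means OA or painful OA.

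The cost is protocol wording, with no new measurement. The sub-study's reference page shows its approval as pending, so the change could be made early. The drawbacks are a slightly narrower interview pool and small pain-by-OA subgroups, whose results should be presented as descriptive.
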